#### 3.2. Sample Size and Power

Approximately 40 participants will be screened to achieve an estimated total of 36 evaluable participants.

For the sample size calculations, the primary endpoint of  $AUC_{24\text{-hour } U_{ox}}$  from Day 90 to Day 180 based on percent change from baseline was used. The group sequential design with pre-specified alpha spending for interim analysis and final analysis was utilized. The randomization ratio is 2-to-1 (active-to-placebo). The primary hypothesis to be tested is a one-sided superiority hypothesis at the significance level of 0.025. The  $AUC_{24\text{-hour } U_{ox}}$  in the placebo arm is assumed to be 0, as the  $U_{ox}$  values may oscillate up and down from baseline due to measurement variability. The  $AUC_{24\text{-hour } U_{ox}}$  in the active arm is assumed to be 3600 based on a 40% decrease over the 90 days. The effect size is assumed to be 1.2. Under these assumptions, the sample size of 36 patients (24 in the active arm and 12 in the placebo arm) will yield a power of approximately 94%. All calculations were performed using [REDACTED].

The above sample size calculation was performed under the assumption that there may be an interim analysis to re-estimate sample size after two-thirds of participants complete the study. However due to late enrollment experienced in the study, an interim analysis will not be performed.

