##### **Treatment Period 24-hour Urine Collection Completeness:**

As detailed in the Study Unblinded Clinical Monitoring Plan, certain members of the unblinded study team will conduct an ongoing review of treatment-period 24-hour urinary creatinine excretion values, to ensure all weight-adjusted 24-hour urinary creatinine excretion values are no more than 20% of baseline. If the percentage change in any weight-adjusted 24-hour urinary creatinine excretion values are more than 20% of baseline, then this is a violation of the completeness criteria. If weight is missing at a visit, LOCF (last observation carry forward) weight should be used in creatinine excretion values per kg calculation. Baseline is defined as the mean of the 2 screening values. Additionally, the site will review the 24-Hour Urine Collection Schedule worksheets completed by the participant. Any collection with a duration of less than 22 hours or greater than 26 hours will be considered invalid.

Should a treatment-period value not meet these criteria, participants will be required to complete another 24-hour urine collection. Recollection should occur within 10 calendar days from the time of the visit for which the collection was intended whenever possible. In the event the repeated 24-hour urine collection violates the completeness criteria, the 24-hour urine collection for that visit will not be repeated a second time.

For the analyses of AUC related endpoints, only 24 hour urine oxalate measurements that meet the completeness criteria will be used for each visit to calculate AUC. That usually would be the latest measurement in case of recollection if criteria are not met. In case there is more than one measurement that does not violate the completion criteria, the average will be taken.

Measurements that violate the completeness criteria will not be included in the AUC calculations. Rather those values will be treated as missing data and will be imputed via the MI methods described in section 6.1.5.1 prior to calculating the AUC values for analysis.

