### 7.2. Protocol Violations and Deviations

Prior to database lock and unblinding, all protocol deviations will be reviewed and categorized as either 'Important' or 'Non-important':

- Important PDs are a subset of protocol deviations that may significantly impact the completeness, accuracy, and/or reliability of key study data or that may significantly affect a subject's rights, safety, or well-being.
- Non-important PDs will be identified as any protocol deviation that does not meet the criteria for Important PD.

Subjects with at least 1 deviation classified in the major protocol deviation list included in the appendix to this SAP will be excluded from the PP analysis population.

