## Major Protocol Deviation List

| Deviation Category        | Deviation Description   | Date Deviation Added | Exclude from Per Protocol Population  |
|---------------------------|---|----------------------|---|
| Informed consent criteria | Subject did not sign informed consent before the initiation of study procedures (including deviations regarding protected health information / data protection forms (e.g. PHI, PIPEDA etc.)  | 16 Mar 2021          | No  |
| Eligibility criteria      | 
Subject was randomized without meeting one or more entry criteria
 
 
1. Genetically confirmed PH
 
2. Uox >0.7
 
3. Less than 20% variation in Ucr
 
4. eGFR >30
 
5. Agree to use contraception and not pregnant
 
6. Prior renal/liver transplant
 
7. Dialysis
 
8. Pox>30
 
9. Systemic oxalosis
 
10. Intercurrent illness
 
11. Active liver disease
 
12. Alcohol/Drug of abuse intake
 
13. Serious mental illness
 
14. Relevant history of disorders including dermatitis and connective tissue disorder
 
 | 16 Mar 2021          | 
 
1. Genetically confirmed PH -Yes, those not confirmed with PH should be excluded
 
2. Uox <0.7 should be excluded - Yes
 
3. More than 20% variation in Ucr should be excluded- Yes
 
4. eGFR <30 should be excluded- Yes
 
5. Agree to use contraception and not pregnant – No
 
6. Prior renal/liver transplant should be excluded- Yes
 
7. Dialysis should be excluded - Yes
 
8. Participants with Pox>30 should be excluded- Yes
 
9. If they have Systemic oxalosis should be excluded - Yes
 
10. Intercurrent illness - No
 
11. Active liver disease - No
 
12. Alcohol/Drug of abuse intake – No
 
13. Serious mental illness- No need to exclude if not affecting urine collection
 
14. Relevant history of disorders including dermatitis and connective tissue disorder - No
 
 |

| Deviation Category           | Deviation Description  | Date Deviation Added | Exclude from Per Protocol Population  |
|-------------------------------------|---|-----------------------------|--|

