| Concomitant medication criteria | The subject used prohibited concomitant medications or therapies   | 16 Mar 2021                 | Yes, for medications that can affect efficacy (e.g. Lumasiran, vitamin C)

No, for medications that can affect safety (e.g. acetaminophen) |
| Efficacy evaluation criteria    | Subject is missing 2 or greater Uox assessments during the period from day 90 to day 180

Subject is missing 3 Uox assessments in a row at any given point                                     | 16 Mar 2021                 | Yes  |
| Efficacy evaluation criteria    | Subject has greater than 20% variance in 2 or greater Uox assessments during the period from day 90 to day 180

Subject has greater than 20% creatinine variance in 3 Uox assessments in a row | 16 Mar 2021                 | Yes  |
| Efficacy evaluation criteria    | Subject did not collect 24 hour urine for full 24 hours and did not perform a repeat for 2 timepoints between day 90 to day 180 or 3 times in a row  | 16 Mar 2021                 | Yes  |
| Safety monitoring               | Subject is a child-bearing female who missed a pregnancy test prior to dosing and was pregnant on the subsequent pregnancy test.   | 16 Mar 2021                 | No   |

| Deviation Category | Deviation Description   | Date Deviation Added | Exclude from Per Protocol Population |
|---------------------------|--|-----------------------------|---|
| Safety reporting          | Subject's SAE was reported late or was not reported  | 16 Sep 2020                 | No  |
| Other criteria            | The subject or site was accidentally unblinded to the subject's treatment information during the study.    | 16 Sep 2020                 | Yes   |
| Other criteria            | Any deviations that constitute fraud, scientific misconduct or Serious Breach will be classified as major. | 16 Sep 2020                 | Yes   |

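### One line of the per-protocol exclusion list sets a 20% limit on Uox assessments without naming creatinine; read literally, it makes PP membership depend on the primary outcome.

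*SAP*

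**What the plan says.** The SAP appendix has an efficacy-evaluation row with two conditions, marked Yes for exclusion from PP. The first is "Subject has greater than 20% variance in 2 or greater Uox assessments during the period from day 90 to day 180". The second is "Subject has greater than 20% creatinine variance in 3 Uox assessments in a row". Only the second names the analyte, and neither says what the 20% is measured against.

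The plan's other 20% urine-collection limits concern urinary creatinine:

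- The treatment-period completeness rule (SAP section 6.1.5.2) reads: "If the percentage change in any weight-adjusted 24-hour urinary creatinine excretion values are more than 20% of baseline, then this is a violation".
- The eligibility part of the same deviation list says "More than 20% variation in Ucr should be excluded- Yes".
- The screening rules in protocol sections 5.1 and 8.1.1.1.1 and in SAP section 6.1.5.2 compare the two creatinine values.

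The list has force through SAP section 7.2: "Subjects with at least 1 deviation classified in the major protocol deviation list included in the appendix to this SAP will be excluded" from PP. SAP section 8.1 repeats the primary analysis in PP; the primary population is MITT. SAP section 5 limits PP exclusions to major deviations that bear on the efficacy endpoint, as judged by the sponsor.

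**The concern.** Percent change in Uox is the primary endpoint, and the drug is meant to lower Uox by well over 20%. A 20% limit on creatinine screens out badly collected samples. The same limit on Uox, measured from baseline, screens out participants in whom the drug worked. The retained participants would be those whose oxalate hardly moved, in either arm, and the PP estimate would be drawn toward zero.

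PP is normally read as a check on the primary result. A near-null PP estimate produced by the exclusion rule could be taken as evidence against a real effect. If the wording were corrected only after unblinding, the correction itself would look data-driven.

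**Working it through.** **Inputs from SAP section 3.2.** The active-arm AUC "is assumed to be 3600 based on a 40% decrease over the 90 days", and "The effect size is assumed to be 1.2". Placebo mean AUC is 0; 24 active and 12 placebo; one-sided alpha 0.025; stated power about 94%.

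**The plan's own figure.** The noncentrality is 1.2 / √(1/24 + 1/12) = 3.394. The normal approximation gives power Φ(3.394 − 1.960) = 92.4%, within 2 points of the stated 94%; a noncentral-t calculation gives 90.9%. The documents give no figure for the PP rule itself.

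**Implied SD.** 3600 / 1.2 = 3000 AUC units, and 3000 / 90 days = 33.3 percentage points. This is the SD of a participant's time-averaged percent change.

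**Share of active participants averaging more than a 20% reduction.** Φ((40 − 20) / 33.3) = Φ(0.6) = 72.6%.

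**From the average to single visits.** The rule counts visits, so the SD at one visit is needed. There are four collections (Days 90, 120, 150 and 180), with trapezoid weights 1/6, 1/3, 1/3, 1/6. The sum of squared weights is 10/36 = 0.278. With a common between-visit correlation ρ, visit SD = 33.3 / √(0.278 + 0.722ρ). The documents do not give ρ, so a range is shown.

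**Applying the rule literally.** Exclude if the change from baseline exceeds 20% in either direction at 2 or more of the 4 visits (normal model, simulated):

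| ρ | Visit SD (points) | Active excluded | Placebo excluded | Excluded among active averaging >20% reduction |
|---|---|---|---|---|
| 0.3 | 47.4 | 94% | 89% | 98.6% |
| 0.5 | 41.7 | 91% | 82% | 98.7% |
| 0.7 | 37.7 | 86% | 73% | 98.9% |
| 0.9 | 34.6 | 80% | 62% | 99.5% |

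**What remains.** Between 20% and 6% of 24 active participants, about 5 down to 1 or 2. Their mean change is about −4% to −7%, against −40% before exclusion. Retained placebo participants stay centred on 0, so the expected PP difference falls from 40 points to about 4 to 7.

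**Two checks on direction.** The Phase 1 reductions quoted in protocol Appendix A.7 (3 mg/kg, mean 67%, range 42% to 80%) all exceed 20%. If the visit SD were only 10 points (an assumption), a single value would breach 20% with probability 97.7% on active (mean −40%) and 4.6% on placebo, so exclusion would follow treatment response closely.

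**With creatinine named.** A change in Uox alone excludes no one. The number excluded would depend on failed collections, for which the documents give no rate.

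**The case against.** The strongest reply is that context settles the meaning. The second line of the cell applies a creatinine limit to Uox assessments, so that term there means the urine collections on which creatinine is checked. The neighbouring rows have the same pairing: two occurrences in the Day 90 to 180 period, or three in a row. On that reading the cell holds one creatinine criterion with two thresholds. This stands as an account of intent. A reader might infer that the sponsor chose Uox response as an exclusion criterion; the documents do not support that.

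A reader might also infer from SAP section 7.2 that any listed deviation removes a participant. The list's own exclusion column contradicts this: late SAE reporting, consent errors and liver-test abnormalities, among others, are marked No. Section 5 adds sponsor adjudication, and section 4.3 places it before unblinding. These safeguards might catch the slip, but they do not cancel the Yes on this row.

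The literal reading also sits badly with blinding. Section 7.2 has deviations reviewed before lock, while section 3.6 withholds on-treatment Uox from the sponsor until then. That supports the creatinine reading without proving it, because section 4.3 allows adjudication after lock.

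Finally, the line gives no reference value. Measured from visit to visit instead of from baseline, stable responders would stay in. Baseline is used above because it is the only reference the SAP gives for on-treatment 20% checks. The gap is a further reason to specify it.

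**Conclusion.** The line is wrong as written and very likely a drafting omission. Taken literally against baseline, it would remove about 80% to 94% of active and 62% to 89% of placebo participants from PP, including about 99% of active participants averaging more than a 20% reduction. These figures rest on the planning mean and SD, a normal model, complete data at four visits, and assumed correlations of 0.9 to 0.3.

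Two stronger conclusions are tempting and not supported. The first is that the trial's main result is at risk. The primary and key secondary analyses use MITT, and the testing hierarchy in SAP section 6.1.4 does not use PP. The bias is toward no effect, so it could not create a false efficacy claim. The second is that only the active arm would be depleted; with the planning SD, most of the placebo arm would go as well. What remains is a flaw in a supportive analysis that should be corrected.

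**What to change.** Before database lock and unblinding:

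1. Reword both lines of the row so that each refers to weight-adjusted 24-hour urinary creatinine excretion differing by more than 20% from baseline, citing the completeness criterion in SAP section 6.1.5.2. Keep the two thresholds: 2 or more collections from Day 90 to Day 180, or 3 collections in a row. Weight adjustment follows the SAP; protocol section 8.1.1.1.1 states the on-treatment rule without it, so the citation should be explicit.
2. Amend SAP section 7.2 so that only deviations marked Yes in the list's exclusion column lead to removal from PP.

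The cost is a few lines of SAP text. No new data are needed, and the primary analysis and sample size are unaffected.

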Should the initial pair of screening values not meet this criterion, participants will be given the opportunity to perform a second pair of collections. The screening period may be extended by 7 days (for a total of 42 days in screening) to allow time to repeat the additional 24-hour urine collections.

[figure not shown]
Additionally, the site will review the 24-Hour Urine Collection Schedule worksheets completed by the participant. Any collection with a duration of less than 22 hours or greater than 26 hours will be considered invalid and must be repeated.

- **Treatment Period 24-hour Urine Collection Completeness:**

As detailed in the Study Monitoring Plan, certain members of the unblinded study team will conduct an ongoing review of treatment-period 24-hour urinary creatinine excretion values, to ensure that all 24-hour urinary creatinine excretion values are within 20% of baseline. Baseline is defined as the mean of the 2 screening values. Additionally, the site will review the 24-Hour Urine Collection Schedule worksheets completed by the participant. Any collection with a duration of less than 22 hours or greater than 26 hours will be considered invalid.

Should a treatment-period value not meet these criteria, participants will be required to complete another 24-hour urine collection. Recollection should occur within 10 calendar days from the time of the visit for which the collection was intended whenever possible (see Figure 1). In the event that the repeated 24-hour urine collection violates the completeness criteria, the 24-hour urine collection for that visit will not be repeated a second time. Statistical considerations for 24-hour urine measurements that violate the completeness criteria are outlined in the Statistical Analysis Plan (SAP).

Figure 1: Timeline Example for Repeat of Treatment-period 24-Hour Urine Collection

8.1.2. 24-Hour Urinary Creatinine Excretion

The completeness of 24-hour urine collections can be assessed by calculating the variability of 24-hour urinary creatinine excretion. Clifford-Mobley et al. suggest that a 20% variability in urinary creatinine excretion exceeds biologic variation and should be considered the upper bound for acceptability of samples ([Clifford-Mobley et al., 2016](#)).

The measurement of urinary creatinine excretion will be via 24-hour urine collection, as described in Section 8.1.1.1.

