## 5. Analysis Populations

The following analysis populations are planned for this study:

- **Randomized Population (RAND):** The randomized population includes all participants who were randomized.
- **Enrolled Population (ENRL):** The enrolled population includes all participants who sign the informed consent form.
- **Safety Population (SAF):** The safety population includes all participants randomly assigned to study intervention and who take at least one partial or full dose of study intervention. Participants will be analyzed according to the intervention they actually received.
- **Intent-To-Treat Population (ITT):** The ITT population includes all participants who were randomized and have at least one postbaseline efficacy assessment. Participants will be analyzed according to the intervention they were randomized to.
- **Modified Intent-To-Treat Population (MITT):** The MITT population includes all participants in the ITT population who have at least one efficacy assessment after the Day 90 dosing visit.
- **Evaluable Population (EVAL):** The evaluable population includes all participants who received 6 full doses of study intervention and completed the study.

- **Pharmacokinetic Population (PK):** The PK population includes all participants in the safety population without major dosing violations. Details will be provided in the PKAP.
- **Per-Protocol Population (PP):** The PP population includes all participants who were randomized and had no major protocol deviations that affect efficacy endpoint assessment as adjudicated by the sponsor.

The primary and the key secondary efficacy analyses will be performed on the MITT population and repeated in further analysis populations as described in section 8.

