### 8.1. Primary Efficacy Analysis

The primary efficacy endpoint of this study is the  $AUC_{24\text{-hour } U_{ox}}$  from Day 90 to Day 180, based on percent change from baseline. The primary endpoint will be compared between the active treatment group and the placebo group.

This is a superiority study. For the primary endpoint, the null hypothesis to be tested is:

- $H_0: AUC_{24\text{-hour } U_{ox, a}} = AUC_{24\text{-hour } U_{ox, p}}$  against one-sided alternative hypothesis
- $H_A: AUC_{24\text{-hour } U_{ox, a}} > AUC_{24\text{-hour } U_{ox, p}}$ .

where

- $AUC_{24\text{-hour } U_{ox, a}}$  is the  $AUC_{24\text{-hour } U_{ox}}$  for the active treatment arm (DCR-PHXC),
- $AUC_{24\text{-hour } U_{ox, p}}$  is the  $AUC_{24\text{-hour } U_{ox}}$  for the placebo arm

All hypotheses will be tested at the one-sided significance level alpha of 2.5%.

Mean  $AUC_{24\text{-hour } U_{ox}}$  from Day 90 to Day 180 will be compared between treatment groups using an ANCOVA model with treatment group as a main effect in the model; and age category [6 to 11, 12 to 17, or  $\geq 18$  years], eGFR category [ $< 45$  mL/min or  $\geq 45$  mL/min], and baseline  $U_{ox}$  as covariates, where the BSA adjustment is applied to the 24 hour urinary oxalate values for all pediatric subjects. The adjusted means for each treatment will be presented together with their 95% confidence intervals. The adjusted mean difference will be presented along with its 95% confidence interval and p-value.

The primary efficacy analysis will be based on the MITT dataset. This analysis will be repeated for the PP population and in addition as sensitivity analyses in ITT and EVAL population (see section 8.5).

$U_{ox}$  concentrations which do not meet completeness criteria (see section 6.1.5.2) will be excluded from the primary efficacy analysis. Multiple imputation will be used for those excluded values as well as for all other missing values.

Descriptive statistics for actual  $U_{ox}$  concentrations and for percent change from baseline will be presented by visit.

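### The per-protocol exclusion row for urine collection uses a full 24 hours, which conflicts with the plan's own 22 to 26 hour validity window and, read literally, excludes participants with valid collections

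*SAP*

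**What the plan says.** On duration, the SAP's treatment-period completeness criteria (6.1.5.2) state: "Any collection with a duration of less than 22 hours or greater than 26 hours will be considered invalid". Protocol 8.1.1.1.1 sets the same limits. A repeat follows only from failure: "Should a treatment-period value not meet these criteria, participants will be required to complete another 24-hour urine collection". For the endpoint, SAP 6.1.5.2 says that "only 24 hour urine oxalate measurements that meet the completeness criteria will be used for each visit to calculate AUC".

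The Major Protocol Deviation List at the end of the SAP uses another limit. One of its efficacy evaluation rows, marked Yes for exclusion from PP, reads "Subject did not collect 24 hour urine for full 24 hours and did not perform a repeat for 2 timepoints" between Day 90 and Day 180, or three times in a row. The row mentions neither the 22 to 26 hour window nor the completeness criteria.

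Two passages govern how the list is used. SAP 7.2, in a sentence that ends by naming the PP population, says: "Subjects with at least 1 deviation classified in the major protocol deviation list included in the appendix to this SAP will be excluded from the". SAP 5 defines PP as randomized participants who "had no major protocol deviations that affect efficacy endpoint assessment as adjudicated by the sponsor". SAP 4.3 places adjudication and the definition of populations after database lock and before the blind is broken.

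The primary analysis is in MITT. SAP 8.1 adds: "This analysis will be repeated for the PP population".

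**The concern.** The exclusion row and the validity rule disagree about what counts as an acceptable collection. A participant who hands in 23.5-hour collections has done what the protocol asks. The values are valid on duration, and if creatinine is acceptable they enter the AUC and nobody requests a repeat. Yet the row's two conditions, less than 24 hours and no repeat, are both met. The repeat condition looks like a safeguard but gives a compliant participant no protection, because a repeat is never triggered.

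The row also errs in the other direction. A collection of more than 26 hours is invalid under both documents but does cover a full 24 hours, so this row does not flag a participant who leaves such collections unrepeated.

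What is at stake is the PP repeat of the primary analysis. With 36 participants planned, a PP set chosen partly by whether home collections stopped slightly before 24 hours loses informative, valid data for a reason unrelated to adherence. It is then a weaker check on the MITT result.

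**Working it through.** **1. The rules side by side**

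| Collection (creatinine acceptable) | Valid under Protocol 8.1.1.1.1 and SAP 6.1.5.2? | Repeat required? | Value used in AUC? | Meets the exclusion row if not repeated? |
|---|---|---|---|---|
| Under 22 h | No | Yes | No | Yes |
| 22 to under 24 h | Yes | No | Yes | **Yes** |
| 24 to 26 h | Yes | No | Yes | No |
| Over 26 h | No | Yes | No | **No** |

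The second and fourth lines are the mismatches. The second leads to exclusion of compliant participants. This step needs no assumption.

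**2. The plan's own figures**

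The documents give no figure for collection durations or for expected PP exclusions, so there is none to reproduce on this point. The nearest is the power of about 94% (SAP 3.2: 24 active, 12 placebo, effect size 1.2, one-sided alpha 0.025). A normal approximation gives Φ(1.2 × √(24 × 12 / 36) − 1.960) = Φ(1.434) = 92.4%, within two points of the stated figure. A noncentral t calculation gives 90.9%. This issue does not change that power.

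**3. How many participants could meet the row**

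Inputs:
- Collections from Day 90 to Day 180: 4 (Days 90, 120, 150 and 180, per the schedule).
- q: the chance that a valid collection lasts 22 to under 24 hours and is not repeated. This is **assumed**; the documents do not give it.
- Visits are treated as independent, also an assumption.

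For the two-timepoint limb, P(at least 2 of 4) = 1 − (1 − q)⁴ − 4q(1 − q)³. For example, at q = 0.2 this is 1 − 0.4096 − 0.4096 = 0.1808.

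The three-in-a-row limb was added by exact enumeration over the six on-treatment collections (Days 30, 60, 90, 120, 150 and 180).

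| Assumed q | 2 of 4 limb | Of 36 | Both limbs |
|---|---|---|---|
| 0.05 | 1.4% | 0.5 | 1.4% |
| 0.10 | 5.2% | 1.9 | 5.3% |
| 0.20 | 18.1% | 6.5 | 18.5% |
| 0.30 | 34.8% | 12.5 | 35.8% |
| 0.40 | 52.5% | 18.9 | 53.9% |
| 0.50 | 68.8% | 24.8 | 70.3% |

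Setting the first formula equal to 0.5 gives q = 0.386. With both limbs the crossing point is 0.378.

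**4. Dependence between visits**

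The same person collects each month, so short collections may cluster within participants. With a beta-binomial and intraclass correlations of 0.3 and 0.6, the 2 of 4 share is 61% and 55% at q = 0.5, 35% and 34% at q = 0.3, and 22% at both values at q = 0.2. Clustering lowers the top of the range and slightly raises the figure at q = 0.2.

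**5. What this would do to the PP repeat**

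Using both limbs, and assuming losses keep the 2:1 ratio, about 29 of 36 would remain at q = 0.2 and about 11 of 36 at q = 0.5. The normal approximation from step 2 then gives power of about 86% and 46%. These figures illustrate the loss of information in the PP repeat only.

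**6. After aligning the row**

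If the row refers to durations under 22 or over 26 hours, a participant whose collections all fall in the window cannot be excluded by it. The share is 0% whatever q is.

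**The case against.** The strongest reply is that the row is loose shorthand. It sits in a list of deviations; a 23.5-hour collection meets the protocol and is not one. Failing to repeat makes most sense where a repeat was due, that is, after a collection that failed the completeness criteria. SAP 5 confines PP exclusion to deviations affecting the efficacy endpoint as judged by the sponsor, and SAP 4.3 puts that judgement before unblinding. A valid value that enters the AUC is hard to call such a deviation. Nor can SAP 7.2 be applied mechanically, because the list it cites contains many rows marked No.

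This has force: sensible adjudication could avert some or all of these exclusions. But the row does not state the window, SAP 7.2 reads as automatic, and nothing written tells the adjudicators to substitute the 22 to 26 hour limit. Relying on them means overriding a listed rule case by case in what the SAP describes as an a priori plan.

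Two stronger readings are not supported:

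- A reader might infer that most compliant participants would be removed. That needs about 39% or more of valid collections to last under 24 hours, and the documents give no durations. Collections of 24 to 26 hours are untouched.
- A reader might infer that over-long collections stay in the PP analysis as data. They do not. SAP 6.1.5.2 and 8.1 drop values that fail completeness from the AUC and impute them, and PP repeats that analysis. The participant may remain; the invalid value does not. The list's separate row on missing assessments might also catch such participants, but it does not say whether values set to missing count.

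It is also fair that PP is supportive. It is outside the testing hierarchy in SAP 6.1.4, and SAP 8.5 provides further checks, including ITT, EVAL, all values regardless of completeness, and MNAR imputation.

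**Conclusion.** The inconsistency is real and follows from the text alone: the PP exclusion row uses a duration limit that neither document uses for validity. Read literally, two valid 22 to under 24 hour collections from Day 90 to Day 180, or three in a row, exclude a participant who complied with the protocol.

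The number affected is unknown. On assumed shares of 10% to 50% of valid collections under 24 hours, with independent visits, it runs from about 5% to 69% on the two-timepoint limb. The three-in-a-row limb adds at most about 1.6 points. These figures also suppose that adjudication does not intervene.

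The consequence is confined to the PP repeat of the primary analysis. The MITT result, its stated power and the testing hierarchy are unaffected. The failure to flag unrepeated collections over 26 hours is a secondary gap in the row, since those values are already removed from the AUC. The row should be corrected, but the primary inference does not depend on it.

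**What to change.** Before unblinding, reword the row to the plan's own limit: *collection duration under 22 or over 26 hours (SAP 6.1.5.2) with no valid repeat, at 2 or more timepoints between Day 90 and Day 180, or at 3 consecutive timepoints.*

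At the same time, reconcile SAP 7.2 with SAP 5 and with the list's Yes/No column. For example, state in 7.2 that only deviations marked Yes lead to PP exclusion, and say what the sponsor's adjudication may and may not change.

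The cost is one reworded row and one clarified sentence in the SAP. No new data are needed: sites already review collection duration from the participants' worksheets, and the primary analysis does not change.
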